6.1.1.2 Sensitivity Analyses

As a method to assess the sensitivity of the primary imputation method for the coprimary endpoints, further imputation methods will be used to impute Week 16 data in subjects who:

- Discontinue treatment or study prior to Week 16
- Have missing Week 16 endpoint data for any reason

The coprimary endpoints will be analyzed using the primary analysis method for each sensitivity imputation method described below:

Last Observation Carried Forward (LOCF)

The last observed post-baseline value will be carried forward and used as the Week 16 value. Subjects without a post-baseline will be considered a nonresponder.

LOCF and NRI

Subjects randomized to the placebo group will have the endpoint value imputed using LOCF (post-baseline). If a placebo subject does not have a post-baseline values, they will be considered a nonresponder. Subjects randomized to BMS-986165 6 mg QD will have their endpoint value imputed using the NRI methodology.

Tipping Point Analysis

Tipping point analysis will further be used to assess the robustness of the primary study results. Different number of events between treatment groups will be assessed until the study conclusion is changed. Each imputed value is initially imputed as a responder. The imputed values in the placebo group will remain as responders while the BMS-986165 imputed values are replaced as a nonresponders one at a time, therefore changing the number of events between groups. Once all imputed values in the BMS-986165 group have been replaced with nonresponders values, the data will reset to where the BMS-986165 group imputed values are all responders and one by one the imputed values in the placebo group are replaced with a nonresponder until all placebo are nonresponders and all BMS-986165 are responders. Furthermore, every pair of imputations between the placebo and BMS-986165 groups will be assessed similarly, creating a matrix of possible patterns. Missing values in the placebo group will be imputed as responders while missing values in the BMS-986165 arm will be imputed as NRI as defined in 6.1.1.1.

At each iteration, the statistical analysis is assessed, and the direction of the analysis is recorded. A graph will be provided to identify at what point to which the difference in events cause a direction shift in study results. The tipping point analyses will be based on a two-sample chi-square test approach rather than a stratified CMH test approach for simplicity of the analysis.

Figure 1: Example of Tipping Point Analysis Direction Boundary

[figure not shown]

Figure 1 represents an example of the tipping-point analysis for all subjects with missing primary efficacy endpoint (responder/non-responder) in BMS-986165 group (N=5) and placebo group (n=5). Gray cells represent pairs where the statistical analysis resulted in non-significance. Green cells represent pairs where the statistical analysis resulted in significant difference between groups. The tipping-point boundary is where the green cells become gray.

Multiple Imputation

Multiple imputation (MI) will be used for sensitivity analyses for each of the coprimary efficacy endpoints, PASI 75 response at Week 16 and sPGA 0/1 response at Week 16. Multiple imputation of missing data for PASI 75 response and sPGA 0/1 response will be performed by fully conditional specification (FCS) using PROC MI in SAS with the FCS option. The FCS MI specifies the multivariate imputation model on a variable-by-variable basis by a set of conditional densities. For each missing value at Week X, the FCS MI will generate values from a conditional distribution for the missing data given the other data prior to Week X. The FCS MI model will include treatment group and stratification factors for randomization. A total of 1000 imputed (complete) datasets will be generated for the MI analysis. The same test procedure used for the main analysis (CMH test), will be used to analyze the responder endpoint from each imputed dataset. SAS PROC MIANALYZE will be used to pool the results from the CMH tests and generate an overall result by Rubin's rules (1987).

6.1.1.3 Supportive Analysis

The coprimary endpoints will be analyzed for the PPS at Week 16 using the primary analysis methodology and primary imputation method.

6.1.2 Key Secondary Endpoints

Analysis Model

CMH tests will be used to compare response rates between BMS-986165 6mg QD and placebo. The following stratification factors from IRT are included in the model: country (mainland China, non-mainland China) and prior biologic use (yes/no). The odds ratio (ratio of odds in BMS-986165 6 mg QD group to the odds in the placebo group) and the corresponding 2-sided 95%

Sponsor: Bristol-Myers Squibb
Protocol no: IM011065

CIs and p-values will be reported. Additionally, treatment differences in proportions and the 95% CI for the treatment difference will be provided.

Imputation Methodology for Week 16 Endpoints

NRI will be used for key secondary efficacy endpoints for subjects who:

- Discontinue treatment or study prior to Week 16
- Have missing Week 16 endpoint data for any reason

Imputation Methodology for Week 52 Endpoints

The key secondary endpoints included in this analysis are the following:

- sPGA 0/1 response with at least a 2-point improvement from baseline at Week 52 and at Week 16
- PASI 75 response at Week 52 and at Week 16

Subjects must meet response criteria at both Weeks 16 and 52 in order to be considered a responder. Those who do not meet response criteria at both weeks will be considered a nonresponder.

NRI will be used for key secondary endpoints for subjects who:

- Discontinue treatment or study prior to Week 52
- Have missing Week 52 data

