• Assess whether BMS-986165 is superior to placebo at Week 16 in the treatment of subjects with moderate-to-severe plaque psoriasis	• sPGA 0/1 • PASI 75
Selected Secondary Endpoints	
• Assess whether BMS-986165 is superior to placebo over the first 16 weeks of treatment	• sPGA 0/1 [REDACTED] • PASI 90 • sPGA 0 • PASI 100 [REDACTED]
• Evaluate improvement in patient reported outcomes for BMS-986165 compared with placebo through Week 16	• Change from baseline in Psoriasis Symptoms and Signs Diary (PSSD) symptom score [REDACTED] [REDACTED] • PSSD symptom score of 0 (among subjects with a baseline PSSD symptom score ≥ 1) [REDACTED]

Overall Design:

This will be a 52 week, multicenter, randomized, double-blind, placebo-controlled study in subjects with stable moderate-to-severe plaque psoriasis. Subjects will undergo screening evaluations within 28 days prior to administration of study treatment to determine eligibility. Following the screening process, approximately 219 subjects will be randomized in a 2:1 ratio to either BMS-986165 6 mg QD or placebo, respectively.

Randomization should not occur until at least 8 days after the screening visit to allow collection of PSSD data during screening in order to calculate a baseline PSSD score. Randomization will be stratified by country (mainland China vs. non-mainland China) and previous biologic use (for psoriasis, psoriatic arthritis or other inflammatory diseases only; yes/no).

At Week 16, subjects randomized to placebo from screening through the Week 16 visit will be switched to BMS-986165 6 mg QD through Week 52 in a blinded manner, so that subjects who had been randomized to placebo will not know if they had been randomized to BMS-986165 or to

placebo post-screening. Subjects randomized to BMS-986165 6 mg QD will continue their current dose through Week 52.

At Week 24, a subject with sPGA ≥ 3 may be treated with restricted topical medications, such as topical high potency corticosteroids (WHO Classes I-V) but only at this time point and at the discretion of the investigator. This treatment may be continued through end of study.

Subjects who discontinue study treatment early are expected to remain in the study for continued follow-up until Week 52.

Subjects completing 52 weeks of treatment may be eligible to roll over to a separate long-term extension study and be treated with open-label BMS-986165 6 mg QD.

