At Week 24, a subject who has [REDACTED] may be treated with restricted topicals/shampoos as described in [Section 6.7.1](#) at the investigator's discretion. These treatments may be initiated only at Week 24 and not at subsequent time points. A subject who is started on these treatments at Week 24 may use them as needed per the investigator's judgement through Week 52.

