2.5 Changes in Statistical Considerations from the Protocol

The following is a list of the important changes in the SAP from the Statistical Considerations section in the protocol:

- Endpoints are revised and 2-point improvement from baseline criterion is added to endpoints Static Physician's Global Assessment (sPGA), Scalp specific Physician's Global Assessment (ss-PGA), Physician's Global Assessment-Fingernails (PGA-F) and Palmoplantar Physician's Global Assessment (pp-PGA)
- The hierarchical testing order for the key secondary endpoints has been updated. The hierarchy presented here supersedes the one that is in the protocol.
- The two endpoints were removed from the list of key secondary endpoints: Change from baseline in Psoriasis Symptom and Sign Diary (PSSD) symptom score and Palmoplantar Physician's Global Assessment (pp-PGA) 0/1 assessed as a proportion of subjects with a pp-PGA score of 0 or 1 among subjects with a baseline pp-PGA score ≥ 3 .
- Imputation methods were updated to remove the prohibited medication/therapy criteria for binary and continuous endpoints.
- The list of relevant protocol deviations provided in the protocol was updated for determination of the Per Protocol population.
- Logistic regression analyses for binary endpoints were removed as these are similar to the CMH analyses.

• [REDACTED]
• [REDACTED]
• [REDACTED]
• [REDACTED]

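### The Week 52 response rate in SAP 6.1.2 mixes BMS-986165 with the topicals permitted from Week 24, and no visible analysis separates the two

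*SAP*

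**What the plan says.** **Week 52 endpoints (SAP 6.1.2).** There are two: "sPGA 0/1 response with at least a 2-point improvement from baseline at Week 52 and at Week 16" and "PASI 75 response at Week 52 and at Week 16". The scoring rule is: "Subjects must meet response criteria at both Weeks 16 and 52 in order to be considered a responder". Non-responder imputation has two triggers, "Discontinue treatment or study prior to Week 52" and "Have missing Week 52 data". No visit between Weeks 16 and 52 enters the definition, and neither does concomitant treatment.

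**Topicals from Week 24 (Protocol 1.1, 4.1.4, 6.7.1 and 6.7.3; SAP 2.1).** The synopsis allows a subject with sPGA of 3 or more at Week 24 to start restricted topicals, with high-potency corticosteroids as its example, at the investigator's discretion. On duration it says: "This treatment may be continued through end of study". Protocol 4.1.4 agrees: "A subject who is started on these treatments at Week 24 may use them as needed per the investigator's judgement through Week 52". The eligibility criterion is blacked out everywhere except the synopsis. Protocol 6.7.1 writes these agents as an exception to the prohibited list, and 6.7.3 places the provision under rescue medication.

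**Change from the protocol (SAP 2.5).** "Imputation methods were updated to remove the prohibited medication/therapy criteria for binary and continuous endpoints".

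**Per-protocol set (SAP 5.0 and 5.1).** Use of such topicals in the two weeks before the Week 16 assessment excludes a subject from this set, but the set is analysed for the coprimary endpoints only.

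**The concern.** For the sPGA endpoint, a score of 3 or more at Week 24 is non-response by definition. If that subject starts a potent topical and is clear or almost clear at Week 52, the rule gives the same score as for a subject who stayed clear on the tablet alone. The plan itself treats these topicals as able to affect psoriasis evaluation: Protocol 6.7.1 restricts them on that ground, and SAP 5.1 removes recent users from the per-protocol set at Week 16. No comparable safeguard is visible at Week 52, although use may run up to that visit.

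After Week 16 every subject receives BMS-986165, so no concurrent placebo group shows how much topicals contribute. At stake is how the Week 52 rate can be read: as the result of a regimen that may include topicals, or as the result of the drug without them.

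**Working it through.** The plan states no figure on this point, so there is none to reproduce. The check has two parts.

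**1. Does the path exist?** Follow one subject through the visible rules.

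- Week 16: sPGA 0/1 with at least a 2-point improvement. The first half of the criterion is met.
- Week 24: sPGA 3 or more. The synopsis permits restricted topicals. The scoring rule does not look at this visit.
- Weeks 24 to 52: topicals continue. Treatment and study are not discontinued, so the first imputation trigger does not apply.
- Week 52: sPGA 0/1 with at least a 2-point improvement, data present. The second trigger does not apply. The subject is a responder.

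Three rules might have intercepted this subject. The protocol's non-responder rule for prohibited therapy (9.4.2.1) does not clearly apply, because these topicals are an exception to the prohibited list from Week 24. SAP 2.5 has in any case removed that criterion. The per-protocol set does not extend to Week 52.

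For PASI 75 the path differs at Week 24. Eligibility is an sPGA threshold, while PASI also weights area, so a subject can have sPGA 3 with PASI 75 intact. The PASI 75 rate is still mixed with topical use, but sPGA of 3 or more does not show that PASI 75 had been lost.

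**2. How large could it be?** With N subjects on BMS-986165, the number of topical starters counted as Week 52 responders is

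N × r × q × u × s

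- N = 146, from about 219 randomised 2:1 (219 × 2/3).
- r = response rate at Week 16.
- q = share of Week 16 responders with sPGA 3 or more at Week 24.
- u = share of those who start topicals.
- s = share of those who meet the criteria at Week 52.

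The documents give no q, u or s; the values below are assumptions. As a share of the arm, the quantity is r × q × u × s. This is also the amount by which the rate would fall if topical starters were counted as nonresponders.

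*Narrow assumptions:* r = 65% (assumed), q = 5 to 10%, u = 100%, s = 50%.

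- Week 16 responders: 146 × 0.65 = 95.
- q = 5%: 95 × 0.05 × 0.5 = 2.4 subjects, or 1.6 points of 146.
- q = 10%: 95 × 0.10 × 0.5 = 4.7 subjects, or 3.3 points of 146.

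*Wider assumptions:* r = 68.9 to 75.6%, the Phase 2 Week 12 rates for PASI 75 and sPGA 0/1 at 3 mg BID (Protocol 2.1), used here only to size the responder pool (146 × 0.689 = 101 to 146 × 0.756 = 110). Both u and s run from 50 to 100%.

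| q | Low: r = 68.9%, u = s = 50% | High: r = 75.6%, u = s = 100% |
|---|---|---|
| 2% | 0.5 subjects, 0.3 points | 2.2 subjects, 1.5 points |
| 5% | 1.3 subjects, 0.9 points | 5.5 subjects, 3.8 points |
| 10% | 2.5 subjects, 1.7 points | 11.0 subjects, 7.6 points |
| 15% | 3.8 subjects, 2.6 points | 16.6 subjects, 11.3 points |

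Every entry credits the whole Week 52 response to the topical. Some of these subjects might have regained response on the drug alone, so each entry is the most that topicals could explain under its assumptions.

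**The case against.** **Counting outcomes regardless of permitted rescue is a legitimate treatment-policy choice, and SAP 2.5 openly drops the medication criterion.** This stands. The present rule is not an error, and replacing it is not shown to be necessary. What is missing from the visible text is a label saying what the rate measures, and a companion analysis.

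**The two-visit rule already limits the effect.** This stands. Week 16 nonresponders, plausibly most of those who start topicals, can never count, so the true effect may be near the bottom of the range.

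**No confirmatory conclusion changes.** This stands. Topicals start at Week 24, so the coprimary and other Week 16 results are untouched. SAP 6.1.2 calls the Week 52 endpoints key secondary, but they appear neither in the list in SAP 4.1.2 nor in the testing order in Table 1, and SAP 6.1.3 makes no adjustment for additional time points. The visible objectives concern Week 16, and the visible text makes no claim of durability. A reader might infer that the trial sets out to prove maintenance of effect and fails; the documents do not support that reading.

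**Text is missing.** This also stands. Four bullets in SAP 2.5 are blacked out, SAP 6.1.5 is not shown as a current section, and a column of Appendix 1 is empty. A rescue analysis could sit there, so its absence cannot be asserted.

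A reader might further infer that the column of subjects switched from placebo is inflated more than the original arm, because they reach Week 24 after only 8 weeks on drug. The two-visit rule does not support this: a switched subject counts only if already a responder on placebo at Week 16. Period 2 by-visit summaries are a separate matter. Their imputation rules are not visible, the documents do not show that more switched subjects would start topicals, and after 8 weeks on drug some would be expected to respond later without them. No size is claimed for that column.

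**Conclusion.** The concern holds on the visible text, within limits. The Week 52 sPGA 0/1 rate can include subjects who were nonresponders at Week 24 and met the criterion again on added topicals. The PASI 75 rate can include topical users, without any implication that PASI 75 had been lost. Compared with counting topical starters as nonresponders, the present rule can only give the same rate or a higher one.

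The size is not derivable from the documents. The 1.6 to 3.3 points and the 0.3 to 11 points both rest on assumed rates of relapse, topical use and recapture; the wider range also borrows Week 12 response rates from Phase 2. This is a matter of interpretation and a cheap improvement, and it does not threaten the trial's primary conclusion.

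**What to change.** Unless the blacked-out or unshown text already does so, amend the Week 52 part of SAP 6.1.2 before the final database lock:

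1. Label the present analysis as *regardless of permitted Week 24 topical use*.
2. Add a second analysis of the same two endpoints. Set to nonresponder any subject who started restricted topicals under the Week 24 provision. For consistency, do the same for any subject who started a prohibited psoriasis therapy before Week 52; otherwise permitted topicals would count against a subject while a prohibited biologic would not. Show shampoo-only users separately, since the criterion for shampoos is blacked out and may differ from that for topicals.
3. Tabulate Week 24 topical and shampoo users by treatment column beside the Period 2 efficacy summaries.

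Concomitant medication is already recorded at every visit through Week 52, and SAP 1.0 foresees an updated SAP before final lock. The cost is one derived flag, one extra table and a second, slightly lower Week 52 rate. The rescue provision itself is not changed.

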6.1.3 Adjustment for Multiplicity

The study hypothesis to be tested is to assess if the odds of achieving both sPGA 0/1 response and PASI 75 response at Week 16 in subjects receiving BMS-986165 6 mg QD are statistically greater than subjects receiving placebo. Each coprimary endpoint will be tested at a 2-sided Type I error = 0.05. Both endpoints need to demonstrate statistical significance to result in a successful study.

- sPGA 0/1 at Week 16: H_{01} : OR = 1 versus H_{11} : OR \neq 1
- PASI 75 at Week 16: H_{02} : OR = 1 versus H_{12} : OR \neq 1

Statistical analysis of the key secondary endpoints will be performed only if both coprimary endpoints are significant. The primary family of coprimary endpoints will be the serial gatekeeper for proceeding with testing of the key secondary endpoints.

In order to control for Type I error rate inflation within the key secondary endpoints, a hierarchical testing method will be implemented. A hierarchical test may only proceed to the next key secondary endpoint if the null hypothesis is rejected at the probability of making a Type I error of 0.05. If an endpoint fails at any step, then all subsequent p-values will be considered descriptive. See Table 1 for Ex-US submission hierarchy.

Table 1: Testing Order of Key Secondary Endpoints

- PASI 90

Sponsor: Bristol-Myers Squibb

Protocol no: IM011065

- ss-PGA 0/1 with at least a 2-point improvement from baseline among subjects with a baseline ss-PGA ≥ 3
- sPGA 0
- PASI 100
- PSSD symptom score of 0 among subjects with baseline PSSD symptom score ≥ 1
- DLQI 0/1 among subjects with baseline DLQI score ≥ 2
- PGA-F 0/1 with at least a 2-point improvement from baseline among subjects with a baseline PGA-F ≥ 3

[figure not shown]
No further multiplicity adjustments will be done for any additional time points or endpoints. Nominal p-values may be provided.

6.1.4 Subgroup Analyses

Subgroup analyses will be performed on the coprimary endpoints using the FAS. The primary imputation method will be applied for these analyses. The CMH test using the stratification factors from IRT will be the analysis method used. The following subgroups will be considered:

- Country (Mainland China, Taiwan, South Korea)
- Sex (male, female)
- Age group (<65 y, ≥ 65 y)
- Body weight (<90 kg, ≥ 90 kg)
- Prior biologic use (yes, no) – from case report form
- Prior systemic treatment of psoriasis (Yes/No)
- Prior phototherapy (Yes/No)
- sPGA (3, 4)
- PASI score (≤ 20 , > 20)
- BSA involvement (10-20, > 20)
- Duration of disease (< 10 y, ≥ 10 y)
- Age at disease onset (<18, 18-39, ≥ 40)

Sponsor: Bristol-Myers Squibb
Protocol no: IM011065

6.2 Safety

Summaries of safety data will be presented by period and treatment group, as applicable, for the As-treated population.

6.2.1 Adverse Events

Adverse events will be presented for the number and percentage of subjects and the number of events. Treatment-emergent will be provided in listings. Summary tables will be reported in decreasing frequency based on the total column. Counting for frequency analysis will be by subject and not by AEs, and subjects are only counted once for recurring AEs within each system organ class (SOC) or preferred term (PT); however, the number of total AEs per subject, including multiple occurrences of individual AEs, will also be presented. For summaries of severity, AEs will be reported only at their maximum severity in each subject. Subjects with multiple AEs within a particular SOC or PT will be counted under the category of their most severe event within that SOC or PT.

AE (including deaths) dates will be imputed according to algorithms detailed in [Section 8.0](#). The imputed date of AE onset will be used to assess whether AEs should be considered as treatment-emergent and included in the safety summaries. The original, partial dates will be included in data listings. No imputation will be performed on missing AE seriousness, severity, or relationship; they will be reported as missing.

AEs will be included in a period if the start date of the AE is after the first dispensation date within a period.

An overall summary for the following categories will be presented:

- Deaths
- SAEs
- Related SAEs
- AEs
- Related AEs
- Discontinued treatment due to AEs

The following summaries will also be provided for the following:

- TEAEs by SOC and PT
- Treatment-related TEAEs by SOC and PT

Sponsor: Bristol-Myers Squibb

Protocol no: IM011065

- TEAEs by PT reported in $\geq 5\%$ of subjects
- TEAEs by PT reported in $\geq 1\%$ of subjects
- Treatment-related TEAEs by PT reported in $\geq 5\%$ of subjects
- TEAEs categorized by severity by SOC and PT
- Exposure-adjusted incidence rate (EAIR) for TEAEs by SOC and PT – EAIR is defined in [Section 8.1](#) of the SAP.

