Procedure	Week 0 Baseline / D1 V2	Week 1 D8 (±3 d) V3	Week 2 D15 (±3 d) V4	Week 4 D29 (±3 d) V5	Week 8 D57 (±3 d) V6	Week 12 D85 (±3 d) V7	Week 16 D113 (±3 d) V8	Week 20 D141 (±3 d) V9	Notes
Fasting Lipid Panel	X				X		X		Subjects are required to fast for at least 10 hours prior to collection
Fasting Plasma Glucose	X				X		X		
Urinalysis	X						X		
Serum Immunoglobulin Levels (IgM, IgG, IgA, IgE)	X				X		X		
Pregnancy Test (Urine)	X			X	X	X	X	X	WOCBP Only
Study Treatment									
Randomize	X								
Dispense Study Treatment	X		X	X	X	X	X	X	
Study Treatment Compliance		X	X	X	X	X	X	X	See Section 6.6

CK = creatine kinase; D = Day; d = days; DLOI = Dermatology Life Quality Index; ECG = electrocardiogram; eC-SSRS = electronic Columbia Suicide Severity Rating Scale; [REDACTED] hs-CRP = high-sensitivity C-reactive protein; Ig = immunoglobulin; [REDACTED] PASI = Psoriasis Area and Severity Index; PE = physical examination; PGA = Physician's Global Assessment; PGA-F = Physician Global Assessment-Fingernails; PHQ-8 = eight-item Patient Health Questionnaire; [REDACTED] PSSD = Psoriasis Symptoms and Signs Diary; [REDACTED] sPGA = static Physician Global Assessment; ss-PGA = scalp-specific Physician's Global Assessment; TBNK = T, B, and natural killer cells; [REDACTED] Wk = Week; WOCP = women of childbearing potential.

Note: All visits ±3 Days

^a In subjects with scalp psoriasis at baseline

^b In subjects with nail psoriasis at baseline

^c In subjects with palmoplantar psoriasis at baseline

When multiple assessments are conducted at a single visit, the following is the order in which they should be done:

- 1) Health outcomes assessments
- 2) Safety assessments
- 3) Clinical efficacy assessments
- 4) Laboratory tests (eg, safety laboratory tests, [REDACTED])

On fasting days, safety assessments can be done first followed by blood draws, and then health outcomes and, finally, efficacy assessments. The dose of the drug on a visit day is to be taken after blood draws.

Table 3: **On-Treatment Procedural Outline (IM011065): Week 24 through Week 52**

Procedure	Week 24 D169 (± 3 d) V10	Week 28 D197 (± 3 d) V11	Week 32 D225 (± 3 d) V12	Week 36 D253 (± 3 d) V13	Week 40 D281 (± 3 d) V14	Week 44 D309 (± 3 d) V15	Week 48 D337 (± 3 d) V16	Week 52 ^a (or early DC) D365 (± 3 d) V17	Safety Follow-up ^b (Week 56) D393 (± 3 d) V18	Notes

Table 3: On-Treatment Procedural Outline (IM011065): Week 24 through Week 52

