6.3.4 Exposure

6.3.4.1 Duration of Treatment

Duration by Group

Overall duration of each treatment, in days, will be calculated for each subject in each treatment group. Subjects are dispensed study treatment at each visit, starting with Day 1 (Week 0) and at each subsequent visit. The date of first dose of study treatment is the Week 0 [redacted] dosing date and is recorded on the eCRF. If this date is missing, then the earliest drug dispensation date will be used. The last dose date is recorded on the end of treatment page in the eCRF. If this date is missing, then the latest date from the [redacted] page or drug accountability return date will be used.

Duration of treatment will be summarized descriptively by treatment group.

BMS-986165:

Subjects randomized to BMS-986165 will have their duration of treatment derived as:

- Date of last dose – date of first dose +1

Placebo:

For subjects randomized to placebo, duration is defined as:

- Placebo = Date of last dose of placebo – date of first dose +1
- BMS-986165 = Date of last dose of BMS-986165 – date of first dose of BMS-986165 +1

Duration by Period

Overall duration (in days) of each treatment received within each study period will be calculated. Duration within each period is defined for each treatment group as:

$$\text{Last dose date} - \text{first dose date} + 1$$

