8.3 Missing, Unknown, or Partial Dates

Start Date		Stop Date						Missing /Ongoing
		Complete: yyyymmdd		Partial: yyyymm		Partial: yyyy		
Partial: yyyy mm	= 1 st dose yyyymm	<1 st dose	≥1 st dose	<1 st dose yyyymm	≥1 st dose yyyymm	<1 st dose yyyy	≥1 st dose yyyy	
	≠ 1 st dose yyyymm	2	1	n/a	1	n/a	1	1
Partial: yyyy	= 1 st dose yyyy		2	2	2	2	2	2
	≠ 1 st dose yyyy	3	1	3	1	n/a	1	1
	Missing		3		3	3	3	3
4	1	4	1	4	1	4	1	1

1 = Impute as the date of first dose

2 = Impute as the first of the month

3 = Impute as January 1 of the year

4 = Impute as January 1 of the stop year

Note: If the start date imputation leads to a start date that is after the stop date, then there is a data error and the start date is not imputed.

Imputation rules for partial or missing stop dates:

1. Initial imputation
 - a. For partial stop date "mmyyyy", impute the last of the month.
 - b. For partial stop date "yyyy", impute December 31 of the year.
 - c. For completely missing stop date, do not impute.

Sponsor: Bristol-Myers Squibb
Protocol no: IM011065

2. If the stop date imputation leads to a stop date that is after the death date, then impute the stop date as the death date.
3. If the stop date imputation leads to a stop date that is before the start date, then there is a data error and the stop date is not imputed.

Imputation rules for partial or missing death dates:

1. If death year and month are available but day is missing:
 - a. If "mmYYYY" for last contact date = "mmYYYY" for death date, set death date to the day after the last contact date.
 - b. If "mmYYYY" for last contact date < "mmYYYY" for death date, set death date to the first day of the death month.
 - c. If "mmYYYY" for last contact date > "mmYYYY" for death date, data error and do not impute.

If both month and day are missing for death date or a death date is totally missing, set death date to the day after the last contact date.

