8.4 Study Periods

Period 1 = Week 0 to Week 16 visit date

Period 2 = Week 16 visit date +1 to Week 52 visit date

Follow-up = 4 week follow-up period

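### As written, the AE period rule in SAP 6.2.1 places Day 1 onsets, and onsets imputed to the first-dose date, in neither study period

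*SAP*

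**What the plan says.** SAP 6.2 presents safety by period and treatment group. The rule in SAP 6.2.1 for placing an AE in a period is: "AEs will be included in a period if the start date of the AE is after the first dispensation date within a period". The same section lets imputed dates decide inclusion: "The imputed date of AE onset will be used to assess whether AEs should be considered as treatment-emergent and included in the safety summaries". One of the start-date imputation codes in SAP 8.3 reads "1 = Impute as the date of first dose".

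On timing, SAP 6.3.4.1 states "Subjects are dispensed study treatment at each visit, starting with Day 1 (Week 0) and at each subsequent visit". It takes the first dose from the Week 0 dosing date and adds a fallback: "If this date is missing, then the earliest drug dispensation date will be used". SAP 8.1 also places the first dose on Day 1. A note to the protocol's Schedule of Activities (Section 1.3, Table 2) says "The dose of the drug on a visit day is to be taken after blood draws".

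SAP 8.4 defines the periods separately: "Period 1 = Week 0 to Week 16 visit date" and "Period 2 = Week 16 visit date +1 to Week 52 visit date", followed by a four-week Follow-up period. SAP 4.2 calls an AE treatment-emergent if it occurs after the first dose and no later than 30 days after the last one.

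**The concern.** The inequality excludes the day on which dosing starts. Protocol 8.2.2 begins collection of nonserious AEs at the start of study treatment, so Day 1 nonserious events are on-treatment events, not screening events to be set aside. Where the SAP wants the first dosing day counted it says so: the concomitant-medication definitions in 6.3.3 and 8.1 use *on or after*.

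The imputation rule makes the gap slightly wider. Code 1 assigns an uncertain onset to the first-dose date, which looks intended to count such events as on treatment. The period rule then omits exactly that date.

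At stake are the Week 0–16 AE tables. They are the only comparison with a concurrent placebo group, because placebo subjects switch at Week 16. A programmer working from 6.2.1 and one working from 8.4 would report different subject and event counts.

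**Working it through.** The plan gives no figure to reproduce, so the check applies the two sets of rules to study days.

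**Inputs**
- Period 1 first dispensing: Day 1 (SAP 6.3.4.1; protocol Table 2).
- First dose: Day 1 (SAP 8.1).
- Week 16 visit and dispensing: Day 113. Week 52: Day 365 (target days, SAP 8.5).
- The Week 16 dispensing opens Period 2. SAP 8.5 starts the first Period 2 window on the day after it.

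**Assignment of an onset on day d.** Under 6.2.1 the lower bounds are d > 1 for Period 1 and d > 113 for Period 2. The upper ends come from 8.4. Under 8.4 alone, Period 1 is Days 1–113 and Period 2 is Days 114–365.

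| Onset day | 6.2.1 as written | 8.4 |
|---|---|---|
| 1 | neither (1 > 1 false; 1 > 113 false) | Period 1 |
| 2 | Period 1 | Period 1 |
| 112 | Period 1 | Period 1 |
| 113 | Period 1 (113 > 113 false) | Period 1 |
| 114 | Period 2 | Period 2 |

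The two rules differ only on Day 1. At the Week 16 boundary the strict inequality gives the right answer.

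**Code 1 imputations.** The imputed onset equals the first-dose date. If dose and dispensing are both on Day 1, this is the first row of the table. If the dosing date is missing, the fallback makes the two dates equal by construction. If dispensing came a day before the first dose, it falls on study Day −1 (SAP 8.1 has no Day 0). Then 1 > −1 holds and the AE is included. The gap therefore needs a shared date, which is the scheduled case.

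**Exposure-adjusted rate (SAP 8.1).** Exposure for a subject with an event is onset date − treatment start date + 1. For Day 1 this is 1 − 1 + 1 = 1 day. The formula treats a Day 1 event as countable.

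**Size.** Period 1 under 8.4 has 113 days. With a flat hazard (an assumption), Day 1 holds 1/113 = 0.88% of onsets. The documents give no AE count. For an assumed 100 to 400 Period 1 AEs over both arms, that is 100/113 = 0.9 to 400/113 = 3.5 events. The number of code 1 imputations is unknown and comes on top.

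**Candidate repairs.** Writing *on or after* for both periods restores Day 1 but moves Day 113 into Period 2 (113 ≥ 113), against 8.4. Using it for Period 1 only, and leaving Period 2 strict, reproduces the 8.4 column on every row.

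**The case against.** The best reply is that the intent can be recovered. The sentence in 6.2.1 says *if*, not *only if*. SAP 8.4 and the exposure formula both point to counting Day 1, and a programmer who uses 8.4 loses nothing. Also, *on or after* is not the SAP's only convention for Day 1: the windows in 8.5 put Day 1 in the baseline row and start Period 1 visits on Day 2. The recoverable intent stands as a reason to rate this minor. It does not remove the inconsistency. An inclusion rule of this kind is normally programmed as necessary and sufficient, and the 8.5 windows govern scheduled assessments, not AE onsets.

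A reader might also infer more than the text supports:

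- *Period 2 AEs are counted in Period 1 as well, because 6.2.1 states no upper limit.* The rule refers to periods, and 8.4 ends Period 1 on the Week 16 visit date.
- *Period 2 might open only at the Week 20 dispensing, leaving four weeks uncovered.* SAP 8.5 opens it on the day after the Week 16 dispensing, and 8.1 is consistent with that.
- *AEs are lost on the Week 16 day.* None are. SAP 8.1 ends Period 1 dosing the day before that visit and starts Period 2 dosing at the dispensing, whereas 8.4 keeps that day's AEs in Period 1. This is at most a side note for reconciliation.
- *The rule favours the active arm.* It is identical in both arms, and nothing in the documents shows a direction.

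**Conclusion.** The rule is wrong as written, with a small effect. Read literally, 6.2.1 removes on-treatment AEs of the first dosing day from the by-period tables, together with code 1 onsets when dose and dispensing share a date. It does so against 8.4 and the SAP's own exposure formula.

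The 0.88% rests on a flat hazard. Real Day 1 onsets could be more or fewer, since Day 1 is a partial day on treatment and early events may cluster. The effect is zero if 8.4 is programmed. Fatal AEs are listed separately under 6.2.2. Treatment-emergent AEs are also listed, although whether a Day 1 onset qualifies depends on how the *after* in 4.2 is read at date level. That doubt matters mainly for serious AEs, which are collected from consent and so may start on Day 1 before the dose.

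**What to change.** **SAP 6.2.1.** Assign an AE to Period 1 if its onset, imputed where necessary, is on or after the first dose date and no later than the Week 16 dispense date (the Week 16 visit date if that is missing). Assign it to Period 2 if onset is after that date. Leave the period ends and the separate Follow-up period as in 8.4, and state in 8.4 that the same Week 16 anchor date applies, so that the sections agree when visit and dispensing dates differ.

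**SAP 4.2.** Define treatment-emergent as onset on or after the first dose date, excluding Day 1 onsets known to precede the first dose.

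**SAP 8.1 (optional).** Reconcile the period dose dates with 8.4 for the Week 16 day.

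The cost is a wording change in 6.2.1 and 4.2, a clarifying line in 8.4, and a changed inequality with a named boundary date in the derivation program. If 8.1 is also aligned, the period exposure dates need reprogramming. No new data are needed. The downside is that Day 1 onsets that cannot be timed against the first dose will count as treatment-emergent, in both arms alike.
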